#### 4.0 Test Schedule

Tests and procedures	Baseline (<21 days prior to registration)	Radiation Treatment Planning	During Radiation Treatment	End of Radiation Treatment +/- 3 days	1 month post RT +/- 7 days	3 months post RT +/- 14 days	At every clinically indicated follow-up 
Physical examination, weight, ECOG PS	X			X	X	X	X
Neurologic history and examination	X 			X	X	X	X
Document current medications	X			X	X	X	X
Pregnancy test	X 						
QOL Assessment: MDASI-BT and BFI 	X 			X	X	X	X 
Standard Mayo glioma brain MRI with and without contrast		X 			X	X	X 
 F-DOPA-PET		X 3,R					
 F-DOPA adverse event assessment		X 					
CT simulation for radiotherapy planning		X 					
Adverse event assessment 	X		X 	X	X	X	X

1. For women of childbearing potential only. Must be done  $\leq 48$  hours prior to injection of study drug. Note: For a positive pregnancy test prior to the pre-RT  $^{18}\text{F}$ -DOPA injection the patient will not undergo the  $^{18}\text{F}$ -DOPA PET scan and will instead be taken off study with no follow-up.
2.  $^{18}\text{F}$ -DOPA post-injection AE assessment: done approximately 40-45 minutes post injection of  $^{18}\text{F}$ -DOPA by the Nuclear Medicine technologist performing the study. If an AE was observed, a second AE assessment is required  $\leq 24$  hours post injection. This assessment will be completed by the study staff. This information will be used for MCCC DSMB review (Section 16.91) and reporting of any AEs under  $^{18}\text{F}$ -DOPA IND (Section 10.0).
3. Must be completed  $\leq 14$  days prior to the start of radiotherapy.
4. CT simulation can be performed prior to or after registration.
5. All follow-up serial imaging after initial treatment will occur until progression or up to 2 years. Typical timing of scans is every 2-3 months or until progression. However, the actual timing of scans for protocol patients will be per the clinician's discretion.
6. To be assessed by Radiation Oncologist at baseline and during radiotherapy and Medical Oncologist for follow-up assessments for MCCC DSMB review (Section 16.91). Adverse events will be assessed weekly during routinely scheduled management visits (+/- 3 days)
7. Maximum grade of adverse events experienced during radiotherapy can be recorded at the end of treatment.

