8. Follow up assessments will be completed as per clinician's discretion
9. Neurologic history and examination will be completed by treating Radiation Oncologist
10. Quality of Life (QOL) and cognitive function will be evaluated with MD Anderson Symptom Inventory Brain Tumor Module (MDASI-BT) and the Brief Fatigue Index (BFI).
11. Patient will be asked to complete questionnaires at baseline and at each MRI evaluation for a maximum of 6 evaluations.

R. Research funded

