#### 7.13 Quality of life

Quality of life (QOL) and cognitive function will be evaluated with the MD Anderson Symptom Inventory Brain Tumor Module (MDASI-BT) and the Brief Fatigue Index (BFI). Every patient will be asked to complete the whole form packet at baseline and at each MRI evaluation for a maximum of 6 evaluations. These time points are selected to capture the quality of life profile and correlate findings with radiologic and clinical progression as well as time points used on prior studies to allow historical comparisons.

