### 13.0 Treatment/Follow-up Decision at Evaluation of Patient

- 13.1 A patient is deemed *ineligible* if after registration, it is determined that at the time of registration, the patient did not satisfy each and every eligibility criteria for study entry. The patient will go off study.
- If the patient received MR and PET for radiotherapy planning, all data up until the point of confirmation of ineligibility must be submitted.
  - If the patient never received pre-RT PET, on-study material must be submitted. No additional follow up is necessary.
- 13.2 Those patients who will not receive any radiation treatment or who will receive radiation treatment elsewhere (not at Mayo Clinic) will be considered non-evaluable for the study endpoint and move to Event Monitoring phase per Section 18.0.
- 13.3 Patients who are CR, PR, REGR, or SD will continue to obtain MRI scans at each clinically indicated follow-up for up to 2 years from registration.
- 13.4 Patients who develop PD or withdraw from further follow-up scans will go to the event-monitoring phase per Section 18.0.

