- 16.83 **Patterns of Failure:** observe patterns of failure after reirradiation using  $^{18}\text{F}$ -DOPA-PET to guide treatment volumes. The MRI scan indicating progressive disease will be fused with our treatment planning scan and the region of progression will be contoured by an investigator blinded to the GTV\_MRI, T2\_FLAIR\_NCET, GTV\_PET, PTV\_high, and isodose lines. A volumetric analysis will then be performed to define the doses delivered to the absolute and relative volume of the region where recurrence is defined.
- 16.84 **Adverse Events:** determine acute and late toxicity after radiotherapy treatment using  $^{18}\text{F}$ -DOPA-PET to delineate treatment volumes. The rate of acute and late treatment-related toxicities for recurrent high-grade glioma patients treated with  $^{18}\text{F}$ -DOPA-PET image-guided radiotherapy will be determined, with acute RT toxicities graded using Common Terminology Criteria for Adverse Events (CTCAE) version 4.0 (available at <http://ctep.cancer.gov>), and late toxicities reported using RTOG/EORTC late toxicity criteria.[39]
- 16.85 **Reoperation Rates:** determine the rate of reoperation for patients undergoing reirradiation for recurrent high-grade gliomas treated using  $^{18}\text{F}$ -DOPA-PET guided volumes. When available, pathologic information detailing the presence of necrosis and/or tumor progression will be recorded.
- 16.86 **Quality of Life:** estimate quality of life (QOL) after radiotherapy using  $^{18}\text{F}$ -DOPA-PET to establish treatment volumes. QOL will be evaluated using the MD Anderson Symptom Inventory Brain Tumor Module (MDASI-BT) and fatigue will be evaluated using the MD Anderson Brief Fatigue Inventory. These questionnaires will be administered at baseline and at each MRI evaluation up to 6 total evaluations to capture quality of life and correlate findings with clinical and radiographic progression. Analysis will include change percent from baseline using t-tests and generalized linear models to test for changes at each time point and non-zero slope.

16.9 **Data Safety Monitoring Plan**

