#### Follow-up Material(s)

CRF	Event Monitoring Phase 		
	Yearly for 2 years	At PD	Death
Adverse Events: Late Toxicities	X	X	
Patient Status: Survival Status Follow-up/ Event Monitoring	X	X	X

1. If a patient is still alive 2 years after registration, no further follow-up is required.

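### After PD or refusal of scans no further MDASI-BT or BFI is provided for, so the later quality-of-life changes and the slope in 16.86 describe only patients without known earlier progression

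*Combined protocol and SAP*

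**What the plan says.** Quality of life and fatigue are secondary goal 2.23. The timing rule in 16.86 is "These questionnaires will be administered at baseline and at each MRI evaluation up to 6 total evaluations to capture quality of life", and footnote 11 of the 4.0 test schedule agrees: "Patient will be asked to complete questionnaires at baseline and at each MRI evaluation for a maximum of 6 evaluations".

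The 4.0 table is more specific. Its QOL row has unqualified marks at end of RT, 1 month post RT and 3 months post RT. Footnote 11 is attached only to baseline and to the column for clinically indicated follow-up. The limit on imaging in footnote 5, "All follow-up serial imaging after initial treatment will occur until progression or up to 2 years", is attached to the MRI entry in that last column only, not to the 1- and 3-month MRIs.

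Section 13.3 says who keeps being scanned: "Patients who are CR, PR, REGR, or SD will continue to obtain MRI scans at each clinically indicated follow-up". Section 13.4 says who leaves: "Patients who develop PD or withdraw from further follow-up scans will go to the event-monitoring phase per Section 18.0". In the event-monitoring table of 18.1 the forms are late toxicities and "Patient Status: Survival Status Follow-up/ Event Monitoring". The two questionnaires appear only in the baseline and active-monitoring tables.

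For the analysis, 16.86 states: "Analysis will include change percent from baseline using t-tests and generalized linear models to test for changes at each time point", together with a test for a non-zero slope. It has no rule for missing forms, progression or death. Section 7.13 gives the purpose of the time points as "to capture the quality of life profile and correlate findings with radiologic and clinical progression", and also mentions historical comparison.

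**The concern.** Beyond the 3-month visit, whether a patient supplies a score depends on whether the tumour has already progressed. Section 16.91 expects progression in most patients and says that it commonly brings severe neurologic symptoms near the end of life. The MDASI-BT asks about such symptoms: one-sided weakness, speaking, seizures, concentration. Patients therefore leave the data for a reason tied to the outcome, and t-tests and generalized linear models of observed percent change, as specified, do not allow for that. A mean over those who remain, or a slope through such means, will tend to look better than the experience of all living treated patients.

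The early visits raise a separate question. Section 4.0 schedules them for everyone, while 13.4 and 18.1 can be read as ending them at progression. If sites follow the second reading, part of the 3-month result is lost as well, and scores not collected cannot be recovered later.

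**Working it through.** **Which forms are lost**

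- *Visit showing progression:* its MRI is an MRI evaluation, so the form is due. Exception: 11.414 also counts clinical deterioration, and failure to return because of death or decline, as progression. Such patients may have no MRI visit and so no form.
- *1 and 3 months post RT:* scheduled without condition in 4.0. Under 11.414 any single criterion makes progression, so 13.4 could apply as early as the 1-month scan. Under note 2 of 11.416, confirmed PD needs more than 3 months since RT, radiologic progression on central review, clinical progression, and exclusion of pseudoprogression; otherwise the status is preliminary PD. Section 13.4 does not say which status triggers transfer.
- *Later visits:* once a patient is transferred, no form is listed under either reading.

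**The plan's own figures**

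The plan gives no sample size or effect size for QOL. The 3-month PFS proportions come from 16.2: 20% (null) and 40% (alternative), with 10 then 20 patients, continuing on 2 or more successes and positive on 6 or more. The probability of a positive result is the sum over x = 2 to 10 of P(X1 = x) × P(X2 ≥ 6 − x), where X1 and X2 are each binomial(10, p). This gives 0.1863 at p = 0.20 and 0.8586 at p = 0.40, matching the stated 0.186 and 85.9%.

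**Numbers at 3 months post RT if first or preliminary progression triggers transfer**

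Assumptions: exponential progression and survival; 1- and 3-month post-RT visits at about 2 and 4 months from registration; median survival of 7-10 months (section 1.6).

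- Can contribute at 4 months = progression-free at 2 months = 20 × p^(2/3): 20 × 0.20^(2/3) = 6.8; 20 × 0.40^(2/3) = 10.9. This is a ceiling, because some will die or be too ill to return before the visit.
- Alive at 4 months = 20 × 2^(−4/m): m = 7 gives 13.5; m = 10 gives 15.2.
- Living patients without a form: pairing poor with poor and good with good, 13.5 − 6.8 = 6.7 and 15.2 − 10.9 = 4.3. The opposite pairings give 13.5 − 10.9 = 2.6 and 15.2 − 6.8 = 8.4.

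**Next serial scan, assumed at 6.5 months**

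If everyone whose progression was seen by the 4-month visit has been transferred, contributors number 20 × 0.20^(4/3) = 2.3 to 20 × 0.40^(4/3) = 5.9. Those alive number 20 × 2^(−6.5/7) = 10.5 to 20 × 2^(−6.5/10) = 12.7. If transfer waits for confirmation at a later scan, the loss starts correspondingly later.

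**Direction and possible size at 4 months, under the same transfer assumption**

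Suppose scores are d SD worse after progression and unchanged before it, and ignore deaths. The mean worsening in all patients is d × (1 − p^(4/3)). Among contributors, including those first progressing at that visit, it is d × (1 − p^(2/3)).

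| 3-month PFS | d | All patients | Observed |
|---|---|---|---|
| 40% | 1.0 SD | 0.71 | 0.46 |
| 40% | 0.5 SD | 0.35 | 0.23 |
| 20% | 1.0 SD | 0.88 | 0.66 |
| 20% | 0.5 SD | 0.44 | 0.33 |

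With d = 0 the bias is zero. The values of d are assumptions; the documents give none.

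**The case against.** The strongest reply is that the early visits are already protected. Section 4.0 marks end of RT, 1 month and 3 months without a progression condition, and the end-of-RT form has no MRI attached. Under note 2 of 11.416, a patient who worsens at 1 month is only preliminary PD and would stay in active monitoring. This stands as far as it goes, and it is why loss of the 3-month data cannot be taken as established. It does not settle the matter, because 11.414 and 13.4 allow the other reading.

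A reader might infer that only 4-8 of 20 patients supply 3-month scores (20 × 0.20 to 20 × 0.40) and that the observed mean is the mean of stable patients. The documents do not support that. Those counts are of patients progression-free 3 months after registration, whereas the visit is 3 months after RT ends, and the form at the progression visit is collected. A reader might also infer that 16.86 promises the course of symptoms after progression. It aims to relate scores to progression, which the progression-visit form partly serves.

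The inputs are also mixed: 16.2 bases the 20% on PFS after bevacizumab failure, while the 7-10 months come from reirradiation series in general. The counts are therefore rough. Finally, this is a secondary endpoint in about 20 patients, outside the decision rule, and labelling later results as conditional would answer part of the point. That also stands, but labelling does not resolve the conflict between 4.0 and 13.4 with 18.1.

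**Conclusion.** The point holds for the later visits and the slope: they are estimated in patients not known to have progressed before that visit, and will probably look too favourable for the treated group. The direction is an inference from the symptoms that 16.91 expects; the size depends on how far scores worsen after progression. In the illustration above the gap at 4 months is 0.22-0.25 SD for a 1 SD worsening, and none if progression does not worsen symptoms.

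For the 1- and 3-month forms the finding is an inconsistency, not a demonstrated loss. If 13.4 is applied at first or preliminary progression, about 7-11 of 20 contribute at 3 months post RT with about 13-15 alive, under the assumptions stated. If it is applied only at confirmed PD, these visits are largely intact. The primary endpoint and its decision rule are not affected.

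**What to change.** Reconcile 4.0 with 13.4 and 18.1: state that the end-of-RT, 1-month and 3-month post-RT MDASI-BT and BFI are collected from every living patient who started RT, whatever the PD status and even if scans are refused, with mail or telephone allowed. Add both forms to the event-monitoring table for that window. Worded this way, the early data no longer depend on which progression status triggers transfer, although 13.4 should still say which of 11.414 and 11.416 note 2 it means.

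In 16.86, make the 3-month change in all living treated patients the main QOL result, report completion by progression status at each visit, and label later MRI-linked changes and the slope as conditional on no prior progression.

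The cost is wording in 4.0 (footnote 11), 13.4, 16.86 and 18.1, and one or two more short questionnaires per progressed patient. Some of these patients will be unable or unwilling to complete them, so some selection will remain; the completion table will show how much.

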### 2.2 Secondary

- 2.21 Compare overall survival from reirradiation and overall survival from initial diagnosis with historical controls
- 2.22 Prospectively evaluate toxicity and reoperation rates after reirradiation
- 2.23 Prospectively evaluate quality of life and fatigue using patient reported outcomes

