### MD Anderson Symptom Inventory - Brain Tumor (MDASI - BT)

#### Part I. How **severe** are your symptoms?

People with cancer frequently have symptoms that are caused by their disease or by their treatment. We ask you to rate how severe the following symptoms have been **in the last 24 hours**. Please select a number from 0 (symptom has not been present) to 10 (the symptom was as bad as you can imagine it could be) for each item.

	As Bad As You Can Imagine											
	Not Present	0	1	2	3	4	5	6	7	8	9	10
1. Your pain at its WORST?												
2. Your fatigue (tiredness) at its WORST?												
3. Your nausea at its WORST?												
4. Your disturbed sleep at its WORST?												
5. Your feelings of being distressed (upset) at its WORST?												
6. Your shortness of breath at its WORST?												

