21. Your change in bowel pattern (diarrhea or constipation) at its WORST?																						
22. Your irritability at its WORST?																						

**Part II.** How have your symptoms **interfered** with your life?

Symptoms frequently interfere with how we feel and function. How much have your symptoms interfered with the following items **in the last 24 hours**? Please select a number from 0 (symptoms have not interfered) to 10 (symptoms interfered completely) for each item.

	Did Not Interfere											Interfered Completely										
	0	1	2	3	4	5	6	7	8	9	10	0	1	2	3	4	5	6	7	8	9	10
23. General activity?																						

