Appendix III

**Brief Fatigue Inventory**

STUDY ID# \_\_\_\_\_ HOSPITAL# \_\_\_\_\_

Date: \_\_\_\_ / \_\_\_\_ / \_\_\_\_ Time: \_\_\_\_\_

Name: \_\_\_\_\_  
 Last First Middle Initial

**Throughout our lives, most of us have times when we feel very tired or fatigued. Have you felt unusually tired or fatigued in the last week? Yes  No**

**1. Please rate your fatigue (weariness, tiredness) by circling the one number that best describes your fatigue right NOW.**

0 1 2 3 4 5 6 7 8 9 10  
 No As bad as  
 Fatigue you can imagine

**2. Please rate your fatigue (weariness, tiredness) by circling the one number that best describes your USUAL level of fatigue during past 24 hours.**

0 1 2 3 4 5 6 7 8 9 10  
 No As bad as  
 Fatigue you can imagine

**3. Please rate your fatigue (weariness, tiredness) by circling the one number that best describes your WORST level of fatigue during past 24 hours.**

0 1 2 3 4 5 6 7 8 9 10  
 No As bad as  
 Fatigue you can imagine

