**F. Enjoyment of life**  
 0 1 2 3 4 5 6 7 8 9 10  
 Does not Interfere Completely Interferes

Copyright 1999  
 The University of Texas M. D. Anderson Cancer Center  
 All rights reserved.

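### QOL and fatigue are to be analysed as percent change from baseline on 0-10 scales where 0 is a valid score, with no zero-baseline rule

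*Combined protocol and SAP*

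**What the plan says.** Goal 2.23 is a secondary goal: "Prospectively evaluate quality of life and fatigue using patient reported outcomes". Section 16.86 gives its whole analysis in one sentence, which begins: "Analysis will include change percent from baseline using t-tests and generalized linear models". The stated purpose is to test each time point for change and the slope for a difference from zero. On timing it says: "These questionnaires will be administered at baseline and at each MRI evaluation up to 6 total evaluations".

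The instruments are reproduced in the appendices, and each allows 0 as a substantive answer:

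- MDASI-BT symptom severity, 22 items (Appendix II, Part I): "Please select a number from 0 (symptom has not been present) to 10".
- MDASI-BT interference, 6 items (Appendix II, Part II): "Please select a number from 0 (symptoms have not interfered) to 10 (symptoms interfered completely) for each item".
- BFI severity, 3 items (Appendix III): "Please rate your fatigue (weariness, tiredness) by circling the one number that best describes your fatigue right NOW", on a scale whose 0 means no fatigue.
- BFI interference, 6 items (Appendix III): 0 to 10, anchored "Does not Interfere Completely Interferes".

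The plan does not say whether items, subscale means or totals are analysed, or what happens when the baseline is 0. It states no SD, effect size or power for QOL or fatigue.

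**The concern.** Percent change divides by the baseline score. On a scale where 0 means the symptom is absent, that causes three problems. A patient with a zero baseline has no value and drops out of that comparison. Equal and opposite changes do not cancel. The same change in points counts for far more in a patient with a low baseline than in one with a high baseline.

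With at most 20 evaluable patients (section 16.3), the average can be driven by a few patients with small baselines. What is at stake is the patient-reported evidence for goal 2.23: whether the reported mean change describes what patients experienced, and how much precision is left.

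**Working it through.** **There is no plan figure to reproduce.** The only t-test power statement in the documents (section 16.82) concerns tumour volumes. The checks below use the arithmetic of the metric, then assumed inputs.

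**1. Arithmetic, with no assumptions.** Percent change = 100 × (follow-up − baseline) / baseline.

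| Baseline to follow-up | Points | Percent |
|---|---|---|
| 0 to 3 | +3 | undefined |
| 2 to 4 | +2 | +100% |
| 4 to 2 | −2 | −50% |
| 1 to 3 | +2 | +200% |
| 8 to 10 | +2 | +25% |
| 1 to 0 | −1 | −100% |
| 10 to 0 | −10 | −100% |

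Rows 2 and 3 together average 0 points but (100 − 50)/2 = +25%. One point is worth 100% at baseline 1 and 10% at baseline 10. Improvement cannot go below −100%, while worsening on a single item can reach +900% (1 to 10).

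**2. Single item, assumed inputs.** From the plan: n = 20. Assumed: baseline mean 2 to 4, between-patient SD 2, error SD 1, scores rounded and cut to 0-10, two-sided 5% one-sample t-test, zero baselines dropped for percent change.

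- *Zero baselines.* The SD of an observed score is √(2² + 1²) = 2.24, and scores below 0.5 round to 0. At mean 2, Φ((0.5 − 2)/2.24) = 25%. At mean 4, Φ((0.5 − 4)/2.24) = 6%.
- *Simulation across this range of means:*

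| Quantity | Percent change | Absolute change |
|---|---|---|
| Power, 1-point worsening | 52-75% | 78-83% |
| Power, 1-point improvement | 61-67% | 71-81% |
| Mean change when nothing changes | +2% to +7% | 0 points |

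**3. Other scoring levels, assumed inputs.** The assumptions here are latent SD 2.3; latent baseline mean 1.5, 3 or 5; baseline/follow-up correlation 0.3, 0.5 or 0.7; a shift of +1 or −1 point; and scoring as a single item, a 9-item mean or a 22-item mean. That makes 3 × 3 × 2 × 3 = 54 scenarios.

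- *Zero baselines:* 2.5% to 33% for a single item, 0% to 3.5% for a 9-item mean, and 0% to 1.2% for a 22-item mean. With a latent mean of only 0.5, the two means rise to about 10% and 4.5%.
- *Mean percent change with no true change:* about −0.5% to +15% for a single item, +31% to +67% for the 9-item mean and +29% to +97% for the 22-item mean. A different assumption about item variation gave about +15% to +36% for multi-item means, so the upward bias is robust but its size is not.
- *Power:* on average 62% with absolute change and 48% with percent change. At nominal critical values percent change was lower in 41 of 54 scenarios. After correction for its lopsided type I error it was lower in all 54, by 3 to 31 points.
- *Example* (22-item mean, baseline mean 3, correlation 0.5, 1-point improvement): 71% against 31% nominally, and 68.5% against 51.3% after size correction.

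**The case against.** Several points on the other side have force.

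- **Scoring decides how many patients are lost.** If multi-item means are analysed, few patients start at exactly 0. This stands: the loss is material for single items and small for means. It does not rescue the metric, because the asymmetry and the weighting towards low baselines remain.
- **The wording is open.** Section 16.86 says what the analysis will include, and it can be read as percent change by t-tests plus a separate model on another scale. That is possible, but no other metric is named, so a reader following the text would compute percent change.
- **The power figures are illustrative.** This stands. The plan gives no QOL inputs. Percent change had the higher nominal power in 13 of 54 scenarios (for example 68% against 58.5% for a 22-item mean, baseline mean 5, correlation 0.3, 1-point worsening). That advantage came from a null distribution shifted to one side, and it vanished after size correction (47.9% against 56.3%). A truly proportional effect would narrow the gap.
- **Slope tests.** A reader might infer that the generalized linear models treat up to six scores per patient as independent, so that the slope tests are invalid. The documents do not support that. Section 16.86 gives no correlation structure and does not assume independence. A model with a patient effect or generalized estimating equations would fit the wording. The most one can say is that the structure is unspecified.
- **New toxicity.** A reader might also infer that new toxicity would go unseen in patients with zero baselines. It would not: section 16.84 grades toxicity by CTCAE and RTOG/EORTC criteria, section 10.10 grades fatigue at baseline and in active monitoring, and the stopping rules in section 16.91 use adverse events, not questionnaires.

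**Conclusion.** The concern holds for the choice of metric. That percent change is undefined at a zero baseline, asymmetric, and weighted towards small baselines follows from the formula and the printed scales without any assumption. The size of the effect does rest on assumptions. For a single item with baseline mean 2 to 4, up to about a quarter of baselines are lost, and power for a 1-point change falls by roughly 5 to 25 percentage points, depending on the baseline mean and the direction of change. For multi-item means the loss of patients is about 0-5% in most settings, and up to about 10% when symptoms are very low. Bias and power loss vary widely with the assumed distributions.

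The consequence is confined to secondary goal 2.23. The 3-month progression-free survival decision rule and the safety rules do not use these scores. The point does not extend to a finding that the slope tests are invalid or that toxicity is missed.

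**What to change.** Amend section 16.86 to:

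1. Name the scores analysed: the MDASI-BT symptom severity mean, the MDASI-BT interference mean and the BFI mean.
2. Replace percent change with absolute change from baseline in points.
3. Test time-point changes and slope with a repeated-measures mixed model that has a random patient effect and the baseline score as covariate. This also makes explicit the within-patient correlation that the current wording leaves open.
4. Keep percent change, if it is wanted, as a descriptive summary only, with a stated rule for a zero baseline.

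The cost is a change of wording. The questionnaires, visits and data stay the same. The downside is that results are reported in points rather than percent.
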